#### **Vital Signs, ECG, Physical Examination and Laboratory Data:**

Vital signs (SBP, DBP, heart rate and body temperature), ECG (12-lead ECG, telemetry and Holter), physical examination and laboratory data will be described at each visit/time. Changes from baseline will be described. Abnormal values will be identified in subject's data listings.

#### **Concomitant Treatments:**

Concomitant treatments are coded using the WHO-DRUG dictionary version 2014-3. All treatments continued after the inclusion or appeared during the study will be summarised by Anatomical Therapeutic Class (ATC) and substance name.

#### **Pharmacokinetics:**

Individual and mean concentration versus time will be plotted on linear and semi logarithmic scales. Plasma concentrations and plasma PK parameters will be listed for LR12. Summary statistics of PK parameters including means, geometric means, medians, ranges, standard deviations, coefficients of variation will be presented for each dose.

Analysis of variance models will be applied to the dose normalised and logarithmically transformed pharmacokinetic parameters to investigate possible deviations from dose proportionality

---

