**Part B:**

Group 3: 0.5 mg/kg i.v. loading dose and 0.03 mg/kg/h maintenance dose i.v. over 7 hours and 45 min;

Group 4: 1 mg/kg i.v. loading dose and 0.1 mg/kg/h maintenance dose i.v. over 7 hours and 45 min;

Group 5: 2 mg/kg i.v. loading dose and 0.3 mg/kg/h maintenance dose i.v. over 7 hours and 45 min;

Group 6: 5 mg/kg i.v. loading dose and 1 mg/kg/h maintenance dose i.v. over 7 hours and 45 min;

Group 7: 5 mg/kg i.v. loading dose and 3 mg/kg/h maintenance dose i.v. over 7 hours and 45 min;

Group 8: 5 mg/kg i.v. loading dose and 9 mg/kg/h maintenance dose i.v. over 7 hours and 45 min.

Please refer to Table 1.

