## Study Plan

Single doses of MOTREM (LR12) or matching placebo (Part B) are planned to be administered following a sequential group design in 26 healthy young male subjects aged from 18 to 45 years: Part A (Groups 1 and 2 of 1 subject each) followed by Part B (Groups 3 to 8 of 4 subjects each). For Part A (Groups 1 and 2), one subject each will receive MOTREM. For Part B (Groups 3 to 8) 3 subjects will receive MOTREM and 1 subject will receive placebo (3:1 ratio). Dose escalation to the following scheduled dose will only occur after satisfactory review of all safety and tolerability data by the Safety Review Committee in accordance with Table 1, protocol sections [8.2](#) Rules for dose escalation/progression and [8.3](#) Toxicity rules.

Subjects will be screened within 14 days and may be performed over multiple days prior to entering the study on Day -1. Each subject will receive verbal and written information followed by signing of the Informed Consent Form (ICF) prior to any screening procedures taking place. Subjects will be admitted on Day -1 and on Day 1 of the study each subject will receive MOTREM (LR12). All the subjects from Part A (Groups 1 and 2) and Part B (groups 3 to 8) will be discharged on Day 2 after 24h post-dose (start of infusion). They will attend the unit for a follow-up visit on Day 8±1. The End of Study visit will take place on Day 28±2. All the assessments performed during the study are detailed in the Study Plan (Table 2 and Table 3). Study design features as well as number of subjects may be adapted according to Table 1.

The end of study is defined as the last subject, last visit (LSLV).

[figure not shown]

Figure 1: Study Flow Chart.

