### **Justification of highest dose level**

The anticipated highest dose regimen that will be tested (cohort 8) is a loading dose of 5 mg/kg administered during 15 minutes (20 mg/kg/h) followed by a maintenance dose of 69.75 mg/kg, administered during a period of 7h45 (9 mg/kg/h).

The highest loading dose will be introduced in cohort 6 (Table 3). This dose in mg/kg/h will be 1.3 times lower by HED BS conversion (25.81 versus 20) and 4 times lower if HED BW is used (80 versus 20). For this cohort, the total exposure in a 15 minutes period in mg/kg will be 1.3 times lower on the basis of HED BS (6.45 versus 5) and 4 times lower on the basis of HED BW (20 versus 5).

In a pilot toxicity study (MOT-PT-01), two monkeys received 18.75 mg/kg/h during a period of 24h, meaning 450 mg/kg (Twice higher rate than the maintenance dose planned in cohort 8 if HED BW is considered). In this study no drug-related adverse event was observed. In terms of total dose in a period of one day, cohort 8 individuals will receive 69.75 mg/kg. In comparison to this pilot study, the total dose that will be administered to cohort 8 is around twice lower if HED BS is used (145.2 versus 69.75) and 6 times lower if HED BW is used (450 versus 69.75). In addition, in a GLP cardiovascular function safety pharmacology study (MOT-PT-02), four monkeys received 18.4 mg/kg/h during 24 hours (total dose of 442 mg/kg) and did not show any drug-related adverse event. Therefore, the highest dose is expected to be safe.

Of importance, in order to further minimise the risk to study subjects in study MOT-C-104, the safety of subjects will be monitored closely and escalation to higher dose levels will be allowed only after careful review by the Safety Review Committee of all clinical and laboratory analysis performed in volunteers (see sections 8.2 and 8.3).

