### **15.2.2 Statistical Analysis on PK Parameters**

Serum concentrations will be listed and summarised by time point. The PK parameters will be listed for each subject and summarised for each treatment group using descriptive statistics (N - the number of subjects, arithmetic mean, SD - standard deviation, CV - coefficient of variation, geometric mean, median, minimum, maximum).

Analysis of variance models will be applied to the dose normalised and logarithmically transformed pharmacokinetic parameters to investigate possible deviations from dose proportionality.

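### Loading-phase PK (C0.25h, AUC0-0.25h) is summarised separately for Groups 6, 7 and 8, although all nine active subjects receive the same 5 mg/kg loading infusion; a pooled summary by loading dose should be added

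*Combined protocol and SAP*

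**What the plan says.** Section 15.2.2 (Statistical Analysis on PK Parameters) sets the unit of summary: "The PK parameters will be listed for each subject and summarised for each treatment group using descriptive statistics". The synopsis, under Pharmacokinetics, is looser: "Summary statistics of PK parameters including means, geometric means, medians, ranges, standard deviations, coefficients of variation will be presented for each dose". It does not say whether dose means the loading dose or the whole regimen, so 15.2.2 is the firmer statement. Neither place provides for a summary by loading dose.

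The synopsis gives the first of the top three regimens as "Group 6: 5 mg/kg i.v. loading dose and 1 mg/kg/h maintenance dose i.v. over 7 hours and 45 min". The next two cohorts keep that loading infusion and raise only the maintenance rate, to 3 and then 9 mg/kg/h. Amendment 4 lowers the Group 8 maintenance rate to 6 mg/kg/h and leaves its loading dose alone. The justification of the highest dose level confirms that "The highest loading dose will be introduced in cohort 6". Each Part B group has 3 subjects on MOTREM and 1 on placebo.

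Two planned parameters describe the loading phase alone: C0.25h (synopsis and 15.2.1) and AUC0-0.25h (synopsis only). Section 15.2.2 also plans an ANOVA of dose-normalised, log-transformed parameters for dose proportionality. It states neither the factor nor the dose used for normalising.

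**The concern.** Part B has six groups but only four loading doses. Until the infusion rate changes at 15 minutes, subjects in Groups 6, 7 and 8 are treated identically, and C0.25h and AUC0-0.25h depend on nothing given later. Summarising them by group splits one exposure into three samples of 3.

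This loading infusion has the highest rate in the trial (20 mg/kg/h in Table 8), and the protocol puts it only 1.3-fold below the body-surface equivalent of the highest animal loading dose. Its peak level and between-subject spread are worth describing as well as the data allow. A mean and SD from 3 subjects say little, and three of them side by side can look like a trend across Groups 6 to 8 when the treatment to that point is the same.

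The unstated normalising dose raises a related question. If C0.25h were normalised by a total that includes maintenance drug not yet given, equal concentrations would appear as departures from proportionality.

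**Working it through.** **Counts.** Planned subjects: 2 × 1 + 6 × 4 = 26, as stated in 9.1. Active subjects in Part B: 6 × 3 = 18. Active subjects at the 5 mg/kg loading dose: 3 × 3 = 9, so each group summary uses 3/9, one third. Table 8 agrees for all three groups: 5 mg/kg ÷ 0.25 h = 20 mg/kg/h, and 5 × 70 kg = 350 mg.

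**What can be pooled.** Table 3 places PK samples at predose, T5' and T15' within the loading phase. C0.25h and AUC0-0.25h use only these. Css inf, C8h, AUC0-8h, AUC0-t and AUC0-∞ depend on the maintenance rate and belong by group. Cmax could be pooled only where it falls at the end of loading.

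**Precision of the mean.** The plan states no CV, alpha or power, so there is no precision figure to reproduce. The 95% half-width of a log-scale mean is t(0.975, df) × SD/√n:

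- One group, n = 3, df 2: 4.303/√3 = 2.48 SD.
- Pooled, n = 9, df 8: 2.306/3 = 0.77 SD. Ratio 2.484/0.769 = 3.2.
- Pooled with cohort kept as a factor, df 9 − 3 = 6: 2.447/3 = 0.82 SD. Ratio 3.0.

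The standard error alone improves by √3 = 1.73; the rest comes from the t quantile.

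With log SD = √ln(1 + CV²), the interval as a multiple of the geometric mean is:

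| Assumed CV | Log SD | n = 3 | n = 9 |
|---|---|---|---|
| 20% | 0.198 | 0.61-1.64 | 0.86-1.16 |
| 30% | 0.294 | 0.48-2.07 | 0.80-1.25 |
| 40% | 0.385 | 0.38-2.60 | 0.74-1.34 |

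**Precision of the spread.** The 95% interval for the log-scale SD, from chi-square quantiles, is 0.52-6.28 times the estimate at n = 3 and 0.68-1.92 times at n = 9.

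**Within the ANOVA.** Take the 18 active Part B subjects and one common variance. With group as factor, df = 18 − 6 = 12 and the half-width for one group is 2.179/√3 = 1.26 SD. With four loading levels, df = 18 − 4 = 14 and the half-width at 5 mg/kg is 2.145/3 = 0.71 SD. The gain is 1.258/0.715, about 1.8.

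**Normalising dose.** Total dose in Group 6 is 5 + 7.75 = 12.75 mg/kg. In Group 8 it is 5 + 69.75 = 74.75 mg/kg at 9 mg/kg/h, or 5 + 6 × 7.75 = 51.5 mg/kg at 6 mg/kg/h. If C0.25h were divided by total dose, identical concentrations would give a Group 8 value of 12.75/74.75 = 0.17 or 12.75/51.5 = 0.25 of the Group 6 value. The plan does not say that it will do this; it does not rule it out either.

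**The case against.** Summarising by assigned regimen is a legitimate default, and the plan reports no confidence intervals for PK: 15.2.2 lists N, means, SD, CV, median and range. The intervals above measure how much those summaries can tell; they are not planned output. The one inferential PK step is the ANOVA, where a pooled variance already recovers part of the loss and the gain is about 1.8 times, not 3.2. Individual values are listed, so anyone can pool the nine later, and PK is a secondary objective. All of this stands and limits the weight of the point. What remains is that pooling chosen after seeing the data is weaker than pooling written down beforehand.

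Group summaries are also needed in their own right. Escalation works cohort by cohort (8.2.4), and the interim analysis (15.5) follows cohort 6, before Groups 7 and 8 exist. A pooled table that replaced them would hide drift between cohorts. This stands, so the pooled summary must be an addition.

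A reader might extend the point to the safety readings around T15' and compare zero-event bounds for 3 and 9 subjects. The documents do not support that. Section 15.1 presents descriptive statistics by product (LR12 or placebo) and time point, and uses dose group only to order the individual listings, so no split into threes is stated. Some of those readings, such as the infusion-site check just after loading, may also fall after the rates diverge.

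**Conclusion.** The point holds for C0.25h and AUC0-0.25h only. Under 15.2.2 these are summarised at the highest loading dose from 3 of 9 identically treated subjects at a time. Pooling narrows the interval for the geometric mean about 3.2 times, or 3.0 times allowing for cohort, and about 1.8 times within a pooled-variance ANOVA. These ratios do not depend on the CV; the intervals in the table do, and their CVs are assumed.

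The result also assumes log-normal values, no drift between cohorts, a T15' sample drawn before the rate changes, and no extensions, replacements or optional cohorts at this loading dose. It is the same with or without Amendment 4.

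Two stronger inferences are not supported. The synopsis sentence alone does not mandate the split, because dose is undefined there. And no section says that later loading-dose decisions will rest on the group-wise C0.25h summaries. Severity is minor: a cheap improvement.

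**What to change.** In 15.2.2 and the synopsis:

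- Keep the PK summaries by treatment group, and add a summary of C0.25h and AUC0-0.25h by Part B loading dose (0.5, 1, 2 and 5 mg/kg), pooling Groups 6 to 8 (n = 9).
- For these two parameters, name loading dose as both the dose level and the normalising dose in the dose-proportionality ANOVA.
- State that Css inf, C8h, AUC0-8h, AUC0-t and AUC0-∞ stay by treatment group.

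The cost is a sentence or two and one more table; no new samples or procedures are needed. The downside is the assumption of no drift between the three cohorts, which the retained group summaries let the reader check.

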## 6 INTRODUCTION

MOTREM (formulated LR12) is developed for the treatment of sepsis and myocardial infarction. MOTREM is to be introduced into Phase I clinical studies to assess safety, tolerance, pharmacokinetics, and pharmacodynamic profile.

MOTREM is the formulation of the active ingredient LR12, which is a 12 amino-acid peptide prepared by chemical synthesis. The investigational drug product MOTREM is prepared as a stable lyophilised product of LR12 peptide in sodium citrate and arginine. The powder is to be solubilised with 40 mL of saline solution for injection to yield a clear and colourless solution of LR12 at 10 mg/mL and at pH 5.5.

The manufacturing of MOTREM for administration to humans is in compliance with the principles of good manufacturing practice (GMP).

MOTREM is expected to be administered as a continuous i.v. infusion in the critical care setting for an average duration of 3 to 5 days.

### 6.1 Mode of Action:

The Triggering Receptor Expressed on Myeloid Cells 1 (TREM-1) is an immunomodulatory receptor expressed on innate immune cells (1–4). The biological function of TREM-1 is the amplification of inflammation. In sepsis, this amplification may result in an exuberant and hyperactivated immune state (“genomic storm”) (5), which is responsible for the onset and progression of the disease.

LR12 is a 12 amino-acid peptidic fragment derived from TREM-Like Transcript-1 (TLT-1), a receptor protein belonging to the TREM-1 family. LR12 can bind to (“trap”) TREM-1 ligand and thereby inhibit the amplification of the immune response caused by the activation of TREM-1 both in sepsis and myocardial infarction (6,7).

### 6.2 Pharmacology:

In vitro, LR12 was shown to be a competitive inhibitor of TREM-1, able to inhibit TREM-1-induced activation of several intracellular proteins implicated in inflammation as well as cytokine production by human neutrophils and monocytes in a dose dependent manner. However, the in vitro incubation of LR12 alone with leucocytes in resting conditions did not induce the spontaneous activation of any of the studied intracellular signalling pathways.

As sepsis is a life-threatening disease characterised by a hyperactivated immune response, it is of paramount importance to consider the safety of LR12, when administered in a condition in which the immune system is activated. In every preclinical model of sepsis and septic shock studied, the administration of LR12 was associated with protective effects especially on the intensity of inflammation, cardiovascular system and survival:

In animal models of peritonitis (mouse and rat), a mortality of 90 to 95% was observed within 7 days following the onset of sepsis. The administration of LR12 decreased mortality with a strong reduction (not abrogation) of the inflammatory response markers, sepsis-induced tissue abnormalities and showed protective effects on the cardiovascular system. In a mini-pig model of peritonitis, the administration of LR12 led to a decreased need of vasopressor (norepinephrine) which translates to a substantial protective effect of the cardiovascular system. LR12 also prevented sepsis-induced tissue abnormalities and dysfunctions.

The TREM-1 signalling pathway belongs to the 10 most upregulated pathways during the “genomic storm” that can be observed in patients with septic shock. During experimental Monkey endotoxemia, the administration of LR12 attenuated the endotoxin-induced blood pressure decrease and release of several inflammatory cytokines in blood. The transcription of a wide range of genes related to the “genomic storm” was also attenuated by LR12 administration.

In addition, LR12 was evaluated in animal models of myocardial infarction: In a rat model of myocardial ischemia-reperfusion, treatment with LR12 reduced the ventricular dilation and improved systolic and diastolic ventricular functions. In a mini-pig model of cardiogenic shock, treatment with LR12 was linked to a strong protection of the cardiovascular system and decreasing the infarct size.

For details please refer to the current Investigator’s Brochure.

### **6.3 Rationale for Conducting Study**

The aim of this First-in-Human (FIH) study is to obtain information on the safety, tolerability and pharmacokinetics of single ascending doses of MOTREM in healthy young male subjects.

The rationale for taking MOTREM into further development is the expectation that this compound could be an effective new anti-sepsis therapeutic agent. Prior to initial testing in patients, the safety and the pharmacokinetic characteristics of the drug in healthy humans must be investigated.

Data from this study will help to design subsequent studies in patient populations clinically and therapeutically relevant with this new class of compound.

### **6.4 Risk-Benefit Evaluation**

#### **6.4.1 Potential Benefits**

MOTREM (LR12) will be given to healthy subjects purely for research and development purposes and those subjects receiving IMP will experience no medical benefit except for a general health examination.

#### **6.4.2 Potential Risks**

##### **6.4.2.1 Nonclinical Safety Pharmacology and Toxicology:**

Toxicity studies were only conducted in one species in accordance with ICH guidance documents S6(R1) and M3(R2) as well as to EMA’s guidance on repeated dose toxicity (EMEA/CHMP/SWP/488313/2007). Safety pharmacology also followed the ICH S7A and S7B guidance.

A cardiovascular safety study in Cynomolgus monkeys did not identify any adverse cardio-vascular effect of LR12, when administered as an intravenous infusion of 18-times the expected pharmacologically active dose. In addition, the central nervous and pulmonary systems were explored during the toxicity studies and did not unveil untoward effects.

Receptor binding assays with a wide range of receptors did not show any relevant off target effects in vitro.

A bacterial reverse mutation test (Ames test) and a chromosome aberration test did not show any evidence for genotoxicity of LR12.

Toxicokinetic studies showed dose-dependent kinetics and suggested a clearance of the product within 15 to 30 minutes depending on the dose.

A series of toxicity studies was conducted with LR12 in cynomolgus monkey, as this represents the only relevant species. In the pivotal 14-day toxicology study with the clinical formulation, the administration of LR12 was safe and well tolerated at doses 7.2, 24 and 140 mg/kg/day. No adverse events were observed up to the highest dose level. In addition, a dose of 440 mg/kg/day in a preliminary formulation was found to be safe and well tolerated in a 14-day study.

Severe time dependent adverse events, likely related to immunogenicity, were observed in the low- dose arm of an early toxicity study conducted with an experimental frozen formulation that was diluted with a technical, non USP grade buffer. Further toxicology studies with a suitable buffer or the API alone and with the final clinical formulation did not reproduce these findings.

#### **6.4.2.2 Clinical Studies**

There is currently no clinical experience with MOTREM. Potential risks will be closely monitored for as part of the safety evaluations being performed in this study.

Measures to minimise the risks to volunteers will include:

- Selection of a starting dose well below a dose level for which effects are expected  
Please refer to protocol section [8.4.1](#).
- Sentinel dosing of subjects. Please refer to protocol section [8.4.4](#).
- Progression to next dose level only after evaluation of data from previous groups/cohorts and approval from Safety Review Committee (SRC). Please refer to protocol section [8.2.3](#) and [8.2.4](#).
- Clinical and laboratory monitoring of study subjects. Please refer to protocol section [8.2.2](#) and [12.1.2](#).
- Exposure to study drug limited to 8 hours. Please refer to protocol section [8.4.1](#).

#### **6.4.2.3 Allergic Reactions, Infusion Reactions and Anaphylaxis**

As with all protein products, administration of MOTREM may result in hypersensitivity reactions including anaphylaxis, or infusion site associated reactions.

Subjects will be closely monitored during and after IMP administration for any symptoms of anaphylaxis and other hypersensitivity reactions, including circulatory and/or respiratory changes or arrest, or urticaria, arthralgia, myalgia or other signs of related reactions. Adequate treatment will be immediately available. Infusion-associated AEs may occur, and depending on its type and severity, discontinuation of infusion may be required. Subjects will be informed of early symptoms and signs of hypersensitivity reactions including hives, swollen face, eyelids, lips, or tongue, or trouble with breathing. An acute infusion reaction algorithm will be used to manage infusion related reactions (refer to Appendix [19.2](#)). In this study regular assessments to monitor infusion reactions and infusion site reactions will be done.. A mandatory sentinel dosing strategy of dosing one subject on IMP on the first day will be used

for each cohort. If safety and tolerability is acceptable the remaining subjects of each cohort will be dosed in group sizes of no more than three with a minimum interval of 24 hours between the start of dosing in the first subject on the previous day and the start of dosing on the next day. In addition, during a dosing day, there will be a minimum interval of 60 minutes between the start of (maintenance) dosing in a subject and the start of dosing in the next subject to ensure that reactions can be dealt with promptly. Any reactions will be treated and taken into account in the dose progression/escalation and toxicity rules. If anaphylactic reactions occur the current “UK Treatment Guideline for Anaphylactic Reactions” of the UK Resuscitation Council will be followed (refer to Appendix [19.1](#)).

#### **6.4.2.4 Product-Specific Antibody Development**

LR12 is a peptide derived from a highly conserved human protein; it is expected to have a low immunogenic profile. An exposure to study drug of 8 hours is not expected to result in triggering an immune response in the study subjects. However, the possibility of triggering an immune response against it in humans still exists. Therefore, all subjects will be carefully monitored for 28 days. Should any subject develop ADA against LR12, they will be followed up for at least 3 months or until the antibody response is no longer detected.

